8.0 Research Plan and Procedures

8.1 HYPOTHESIS: Describe the hypothesis or what the study hopes to prove:

Access to healthcare is currently a key priority for Department of Veterans Affairs (VA). Store-and-Forward (SFT) Teledermatology has emerged as an important strategy to enhance the access of patients to high quality skin care within VA. The current practice of teledermatology in VA is effective but has not been uniformly implemented, and inefficiencies in the current workstation-based process may discourage teledermatology adoption by primary care clinics. VA Office of Connected Care's (OCC's) mobile app, *VA Telederm*, has been developed as a more facile and efficient option that may enhance teledermatology adoption among providers.

Once patients establish care in a dermatology clinic, they often need follow-up visits to evaluate responses to treatment and to adjust management, neither of which necessarily requires a face-to-face visit. To address these issues, OCC has additionally developed the *My Telederm* app to allow established dermatology clinic patients to follow-up remotely using their own mobile devices. By reducing the need for some patients to follow-up in person, the app may improve clinic access to in-person dermatology clinics.

The overall hypothesis of this proposal is that sites implementing VA's teledermatology mobile apps will significantly augment the use of teledermatology and improve Veterans' access to skin care relative to control sites. Specifically, we hypothesize that *VA Telederm* will facilitate the implementation and adoption of teledermatology among primary care clinic staff, increasing use by existing programs and potentially expanding teledermatology to new sites while reducing patient travel to dermatology clinics. Additionally, we hypothesize that *My Telederm* will improve established patients' ability to follow-up with dermatology care remotely, while opening up dermatology clinic space for other patients.

8.2 AIMS: List the specific aims:

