Aim 1. Measure impact of apps on access to dermatology care. *San Francisco VA Health Care System's involvement is limited in Aim 1. All data related to this aim is collected by the VA's Center for Access Policy, Evaluation Research (CAPER) located at the Boston VA Health Care System. All data collected from the Corporate Data Warehouse, or any other databases as approved by the Boston VA Health Care System IRB will be anonymously recorded, aggregated, and shared with investigators and study staff at the San Francisco VA Health Care System and other sites. No analysis of the primary data will occur at San Francisco VA.*

Both apps will be made available over a 2 year period in a randomized, stepped-wedge design to Veterans Health Administration (VHA) facilities, after each app becomes available. The *VA Telederm* app will be distributed to 36 eligible VHA facilities that currently have low teledermatology activity and thus have had relatively poor adoption of basic consultative teledermatology. The *My Telederm* app will be distributed to 24 facilities with dermatology clinics that currently have relatively high teledermatology activity and thus already have relatively mature teledermatology programs ready for advanced operations.

By using health factors and stop codes unique to each app, we will use the VA Corporate Data Warehouse (CDW) to measure the impact of both apps on the following outcomes reflecting dermatology access: 1) Consult and appointment completion times for both teledermatology and in-person consults, stratified by new and established patients (primary outcome); 2) Instances of

dermatologic care (associated with either teledermatology or in-person dermatology encounters); and 3) Travel costs for VA, as well as non-VA care consult rates and associated costs. In addition, the following outcomes will be measured specifically for the *My Telederm* app: 1) Proportions of new patient encounters in-person dermatology clinics; and 2) “No-show” rates and timeliness of follow-up. Results of each of these access measures will be stratified to examine the effect on rural/highly rural Veterans, as well as to determine whether a differential effect occurs for facilities with some pre-existing teledermatology relative to those that had none.

Aim 2. Determine the factors that affect personal and organizational adoption of mobile apps.

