VA Telederm is anticipated to be ready for national release in January 2017 and *My Telederm* in the spring of 2018, as part of VA’s Office of Connected Care operations. Beforehand, technical field testing will occur at San Francisco, Providence and Denver VHA facilities. For national rollout, each app will be targeted to sites that are clinically appropriate and best positioned to benefit from the app. Within these sites, the apps will be released in three month intervals according to allow a cross-sectional stepped-wedge cluster randomized trial for each app. We anticipate the affected population will represent VA’s as a whole.

The impact of teledermatology apps depends not only on their intrinsic effectiveness, but also on successful implementation and adoption by as many target sites and end-users as possible who then maintain the practice. Outcomes may be organized within the RE-AIM Framework, which encompasses multiple domains necessary for translating innovation into real-world practice. The Reach and Effectiveness domains are addressed in Aim 1; The Adoption, Implementation and Maintenance domains are the focus of Aim 2.

Aim 1 will assess each app’s effect on Veterans’ access to dermatology in a stepped-wedge cluster randomized trial. Corporate Data Warehouse (CDW) data pertaining to access will be collected remotely by the Center for Access Policy, Evaluation and REsearch (CAPER) under its own IRB approval. Multiple measures reflecting different aspects of access will be evaluated to achieve a comprehensive and accurate evaluation of each app’s impact. Aim 2 will focus on measuring the degree to which each app was implemented. Using semi-quantitative interviews and surveys of key VA staff members at the three early adopter sites (San Francisco, Denver and Providence VA Medical Centers) involved in technical testing as well as data in CDW and OCC databases, we will monitor implementation and identify organizational, individual, and app-specific factors that affect each app’s overall impact.

8.4 BACKGROUND AND SIGNIFICANCE: Briefly provide the background and significance of this study (e.g. why is this study needed) (space limit: one half page):

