Data analysis. Primary data will be collected and analyzed by CAPER and shared in aggregate with the PIs and other investigators. Stepped wedge - cluster randomized trials (SW-CRTs) need to employ data analysis strategies that account for the causal structure implied by this design and mitigate its potential shortcomings. Two related issues which may confound the treatment effect are the within-cluster correlation and potentially significant secular trends in the outcomes of interest given the long duration of the trials (2.5 years). In fact, the exposure of each cluster to both the control and intervention allows the researcher to partially exploit the within cluster variance towards estimation, which renders this type of trial less sensitive to the intra-cluster correlation coefficient. To further ensure that these confounding factors are properly handled, we will analyze the data using mixed models that allow for time fixed effects and cluster random effects.

Second, we are interested in the average effect of the treatment among compliers (patients who only receive the treatment as a direct result of their exposure to the intervention), referred to as the Local Average Treatment Effect (LATE). This effect better reflects the efficacy of teledermatology compared to regular practice. In order to estimate LATE, we will follow an instrumental variable (IV)-based two-stage residual inclusion (2SRI) procedure.

Finally, we will also conduct an intent-to-treat analysis, yielding an estimate of the average effect of being randomized to receive one of the telederm apps (average treatment effect). From a policy perspective, this effect can be interpreted as the efficacy of deploying an app in real-world outpatient clinics, where overall uptake to clinical practice is likely less than 100%.

Aim 2

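### The Aim 1 model in 8.13 has no term for site waits that drift between quarters; if consults are analysed individually, its standard errors would be too small

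*Combined protocol and SAP*

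**What the plan says.** Section 8.3 describes a "cross-sectional stepped-wedge cluster randomized trial for each app", and says that "the apps will be released in three month intervals". Section 8.2 gives 36 sites for VA Telederm and 24 for My Telederm, released over two years. The primary outcome is completion time for consults and appointments.

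Section 8.13 names two threats: correlation within clusters, and secular trends over trials lasting 2.5 years. It argues that each site's exposure to both conditions lets the analysis use within-site variation, "which renders this type of trial less sensitive to the intra-cluster correlation coefficient". Its modelling remedy is then: "we will analyze the data using mixed models that allow for time fixed effects and cluster random effects". No site-by-period term, decaying correlation, robust variance, small-sample correction or sensitivity analysis on this point is stated anywhere in the document.

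The Aim 1 text in 8.13 opens by saying that this plan could not be followed, because too few sites took part during a study that overlapped the COVID-19 pandemic. The investigators looked instead at what predicts completed app consults, and at rural-urban differences.

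**The concern.** One random intercept per site treats two consults in the same quarter as no more alike than two consults at that site two years apart. Waiting times are unlikely to behave that way: staffing and backlog shift from quarter to quarter and affect every consult in the quarter. Period fixed effects remove only the movement that all sites share. The site's own movement goes into consult-level noise, which the model divides by the number of consults. The larger the site-quarter volume, the more the reported precision exceeds the real precision.

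At stake is the intent-to-treat estimate, which the plan presents as the policy-relevant result. Its intervals would be too narrow, and an app with no effect would be declared effective too often.

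**Working it through.** There is no planned figure to reproduce. Section 10.3 says only that power is good for a 10% difference from baseline, without ICC, SD, volume or correlation structure. The check is therefore conditional on assumptions.

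**From the documents.** 36 and 24 sites (8.2), three-month steps (8.3), two-year roll-out (8.2), 2.5-year duration (8.13).

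**Assumed.** The number of steps is not stated. I took 9 steps of 4 sites over T = 10 quarters for VA Telederm, and 8 steps of 3 sites over T = 9 quarters for My Telederm. Total variance is 1 and the test is two-sided at 5%. The within-quarter ICC is ρ, each site-quarter has m consults, and r is the ratio of between-quarter to within-quarter correlation.

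**True structure (nested-exchangeable).** Site variance τ² = ρr; site-by-quarter variance γ² = ρ(1−r); consult variance σ² = 1−ρ. Given the site, a site-quarter mean has variance γ² + σ²/m.

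**Planned model.** With no γ² term, the likelihood fit settles on a residual variance s² = [(T−1)(σ² + mγ²) + T(m−1)σ²] / (Tm−1), and treats the cell mean as having variance s²/m.

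**By hand, 36 sites, ρ = 0.05, m = 150, r = 0.8:**
- γ² = 0.05 × 0.2 = 0.01; σ²/m = 0.95/150 = 0.00633; true cell variance 0.01633.
- s² = [9 × (0.95 + 1.5) + 1490 × 0.95]/1499 = (22.05 + 1415.5)/1499 = 0.959; s²/m = 0.00639.
- √(0.01633/0.00639) = 1.60. The estimate rests mostly on within-site contrasts, so this is nearly the SE ratio.

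**Full calculation.** With D holding the period columns and the treatment column, V_f the fitted covariance and V the true covariance of a site's cell means:
- reported variance = (ΣD′V_f⁻¹D)⁻¹
- true variance = (ΣD′V_f⁻¹D)⁻¹ (ΣD′V_f⁻¹VV_f⁻¹D) (ΣD′V_f⁻¹D)⁻¹

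The same case gives a reported SE of 0.0147 and a true SE of 0.0234, a ratio of 1.59. Actual error = 2Φ(−1.96/1.592) = 2Φ(−1.231) = 21.8%.

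| ICC | m | r | true SE / reported SE | actual error of 5% test |
|---|---|---|---|---|
| 0.05 | 150 | 1.0 | 1.00 | 5.0% |
| 0.05 | 150 | 0.95 | 1.18 | 9.6% |
| 0.05 | 150 | 0.9 | 1.33 | 14.1% |
| 0.05 | 150 | 0.8 | 1.59 | 21.8% |
| 0.05 | 400 | 0.8 | 2.27 | 38.7% |
| 0.01 | 150 | 0.9 | 1.07 | 6.7% |
| 0.01 | 150 | 0.8 | 1.13 | 8.4% |
| 0.05 | 25 | 0.9 | 1.06 | 6.4% |
| 0.01 | 25 | 0.9 | 1.01 | 5.2% |

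The 24-site layout gives the same figures to within rounding.

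**Simulation.** REML fits, 500 trials per cell, ICC 0.05, at (m, r) = (150, 0.9), (150, 0.8) and (400, 0.8). The planned model rejected a null app in 13.8%, 19.0% and 39.0% of trials (36 sites), and in 13.4%, 22.8% and 43.4% (24 sites). With a site-by-quarter effect added, rejection was 3.8% to 5.6%.

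**Cost in precision.** At ICC 0.05 and m = 100 with 36 sites, the planned model reports 0.0179. The right model gives 0.0220 (r = 0.9) or 0.0253 (r = 0.8), that is 0.0220/0.0179 = 1.23 and 0.0253/0.0179 = 1.41.

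**Site-quarter means instead of consults.** The residual then estimates γ² + σ²/m directly, so the SE ratio is 1.00 under the structure above (checked at r = 0.8). If correlation decays as AR(1) with 0.80 to 0.95 per quarter, reported/true SE is 0.77 to 0.98 and the error 5.4% to 13.3%.

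**The ICC sentence.** Take 36 sites, m = 150, r = 0.8 and the right model. Raising the ICC from 0.01 to 0.10 moves the stepped-wedge SE from 0.0165 to 0.0294 (×1.8). For a parallel trial over the same 10 quarters, SE = √{4[τ² + (γ² + σ²/m)/10]/36}:
- ICC 0.01: √[4 × (0.008 + 0.0086/10)/36] = 0.031
- ICC 0.10: √[4 × (0.08 + 0.026/10)/36] = 0.096 (×3.1)

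**The case against.** **The plan was not carried out.** A reader might infer that reported Aim 1 results carry intervals that are too narrow. The documents do not support that: 8.13 says the plan was not followed. This objection stands and limits the point to the plan as written.

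**8.13 is a summary.** The form asks for a brief account, and Aim 1 is analysed by another VA centre under its own IRB approval, which is not in these documents. A fuller model may exist there. That stands as a caution. Still, 8.13 offers this model as the remedy for within-cluster correlation, and nothing in the document adds to it.

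**The unit of analysis is open.** Section 10.1 speaks of aggregate data, while 8.13 defines its complier effect on patients, which points to individual records. With site-quarter means the problem goes away under nested-exchangeable correlation, though not under decay. This stands, and the conclusion is conditional on it.

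**The ICC statement is not wrong.** One might infer that lower sensitivity to the ICC holds only when the correlation is constant over time. It does not: with drift and the right model the SE rises ×1.8, against ×3.1 for a parallel trial. The comparative claim survives and needs only a qualification.

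**Repeat patients.** Section 8.1 says "Once patients establish care in a dermatology clinic, they often need follow-up visits", so one might ask for a patient random intercept for My Telederm. But the design is described as cross-sectional, the records are to be anonymous, and nothing shows how often a patient would recur in the primary outcome. That demand is not supported.

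**Power.** Section 10.3 names no model, so the documents do not show that its power claim rests on this one.

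**Conclusion.** The point holds conditionally. The model as stated implies one constant within-site correlation over 2.5 years. If consults are analysed individually, standard errors are model-based and site waits drift between quarters, the standard errors are too small.

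No size can be derived from the documents alone. Under the assumed layout, the 5% test errs in about 10% to 22% of trials at ICC 0.05 and 150 consults per site-quarter (ratio 0.95 to 0.8). At ICC 0.01 and the same volume it errs in about 7% to 8% (ratio 0.9 to 0.8), and at ICC 0.01 with 25 consults the error is negligible. The 39% figure needs both 400 consults per cell and a ratio of 0.8.

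This is a weakness to correct in the plan and in any stepped-wedge analysis that reuses it. It is not a mandatory correction to results already produced.

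**What to change.** In 8.13:

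- Keep the site random effect and period fixed effects, and add a site-by-quarter random effect, or a within-site correlation that decays with time.
- State the unit of analysis (consult or site-quarter mean).
- Use a small-sample correction (Kenward-Roger or similar), given 24 or 36 clusters. This is a precaution; the figures above do not test it separately.
- As a sensitivity check, obtain the intent-to-treat p-value by permuting the randomised release order.
- Keep the ICC sentence, but add that within-site correlation that changes over time must still be modelled.

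The cost is a few lines of text and slightly longer model fitting. The downside is wider intervals: in the 36-site example above, an SE 23% to 41% larger than the planned model would report.

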Validate a new model for enhancing access to patients. Historically, teledermatology has been principally practiced as a consultative tool where a PCP requests guidance from a dermatologist. The preponderance of published research has similarly focused on consultative teledermatology. However, with the widespread availability of digital cameras and internet access, the ability to accept teledermatology consultations directly from patients has increasingly emerged in commercial ventures but with little scientific validation of their actual impact on healthcare. Within VA, there has also recently been an evolution toward delivering healthcare centered in patients' homes, and OCC has begun live-interactive telehealth encounters with patients in their homes. The effect of this type of telehealth is unknown. The *My Telederm* app will be VA's first attempt to bring store-and-forward telehealth into patients homes and may have significant impacts on not only the patients that it directly serves, but also indirect effects on new patients who need to be seen in person in clinics and who may benefit from the additional capacity created by allowing established patients to follow-up remotely. The proposed research seeks to measure the magnitude of this effect.

Understand factors affecting successful implementation of mobile apps. Implementation and adoption of telehealth, including teledermatology, in the VHA has proven to be a slow and heterogeneous effort, having taken over 8 years since the program was nationally disseminated by VA, with no systematic effort to collect data that would inform VA as to the reasons why teledermatology has been actively adopted and thriving at some sites, while being neglected or failing at others. It is thus significant that the proposed research will be the first large-scale attempt to understand the implementation science associated with a teledermatology program, and it will be the first to study VA apps that are intended to interface directly with existing clinical care pathways. The research will have strategic importance for VA and OCC as additional mobile apps serving other clinical needs, particularly those that directly interact with clinical care of patients, are rolled out in the future. Additionally, we believe that studying the process within the paradigm of OTIE and the REP framework will allow the findings to be broadly applicable to other healthcare organizations.

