If the instruments are not complete or not available because they will be developed as part of this study, describe the basic content or include an outline and submit the final versions to the IRB with a modification for approval prior to use.

- 1) Site Information Report (revision attached)
- 2) Site Process Guide (attached)
- 3) Organizational Readiness for Change (ORC) Survey (revision attached)
- 4) Initial Interview Guide (attached)
- 5) Bi-Monthly Site Report (survey revision attached)
- 6) Follow-up Interview Guide (Allows participants to expand on the same areas covered by the bi-monthly site report)
- 7) Program Sustainability Index (survey revisions attached) Now VA T Program Sustainability index (attached) and My T Program Sustainability index (attached)
- 8) Sustainability Interview Guide (attached-Allows participants to expand on the same areas covered by the PSI survey)
- 9) Bi-Monthly Site Report for National Sites (attached)

Telephone/Email Consent Scripts for Contacting Subjects:

- 1) Email consent script (introduction and consent to ORC, both Bi-monthly reports, and Program Sustainability Index surveys)
- 2) Telephone consent script (introduction and consent to Site Process Guide, Initial Guide, Follow-up Guide, and Sustainability Guide)

Attach any unpublished instruments in the 'Other Study Documents' section of the Initial Review Submission Packet form after completing the study application. Published instruments should NOT be attached.

8.12 * BIOSPECIMEN COLLECTION: Are you drawing any blood or collecting other biosamples (e.g. tissue, buccal swabs, urine, saliva, hair, etc.) for analysis under this protocol and/or storage for future research: (REQUIRED)

Yes No

8.13 STATISTICAL METHODS: Briefly summarize the methods and types of analyses that will be performed:

Aim 1-Due to a lack of participation by sites during the study which was in part conducted during the novel coronavirus (COVID-19) pandemic, we were not able to follow the analysis plan for Aim 1 described below. Instead we focused on understanding factors associated with successful completion of consults with the mobile apps, examining differences between rural and urban Veteran users.

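### Does My Telederm's hypothesised benefit to non-users invalidate the planned complier-effect analysis?

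*Combined protocol and SAP*

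**What the plan says.** For Aim 1, Section 8.13 lists three elements: mixed models with time fixed effects and cluster random effects, a complier effect (LATE) by instrumental variables with 2SRI, and an intention-to-treat (ITT) analysis of being randomised to an app. On the second it states that "we are interested in the average effect of the treatment among compliers". Compliers are defined at patient level. Of the complier effect the section says "This effect better reflects the efficacy of teledermatology compared to regular practice". It states no identifying assumptions and does not separate the two apps.

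My Telederm is described in Section 8.1 as a tool to "allow established dermatology clinic patients to follow-up remotely using their own mobile devices". The hypothesis there is that it will help those patients "while opening up dermatology clinic space for other patients". Section 8.4 mentions "indirect effects on new patients who need to be seen in person in clinics and who may benefit from the additional capacity" and makes the size of this effect something the research seeks to measure.

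The primary outcome in Section 8.2 is completion time for teledermatology and in-person consults, stratified by new and established patients. A further My Telederm outcome is "Proportions of new patient encounters in-person dermatology clinics".

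Section 8.13 opens its Aim 1 text with the statement that "we were not able to follow the analysis plan for Aim 1 described below". The reason given is poor site participation, partly during the COVID-19 pandemic. The replacement is a study of factors linked to completing consults with the apps, comparing rural and urban users.

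**The concern.** An instrumental-variable estimate divides the effect of site exposure by the uptake that exposure produces. The result is a user effect only if exposure does nothing to people who do not use the app. For My Telederm the protocol hopes that exposure will help such people, and it wants to measure by how much. The complier analysis therefore has to assume away a path that the study sets out to find.

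If the path exists among the analysed patients, benefit to non-users is credited to users, and the lower the uptake, the larger the error. Because Section 8.13 presents the complier effect as the better guide to efficacy, a reader could take an inflated per-user benefit as the main message. Two further oddities follow. New patients cannot be My Telederm users, so that stratum has no complier effect at all. And the new-patient share of encounters is a clinic-level quantity, for which no individual complier is defined.

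**Working it through.** The plan gives no figure for the complier effect, uptake or spillover, so there is nothing to reproduce. The check is algebra with assumed values.

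**Inputs**
- p, the share of analysed patients who use the app because their site has it: not given. Section 8.13 says only that uptake is likely below 100%.
- s, the effect of release on a non-user: not given.
- d, the full effect of release on a user: not given.
- 24 My Telederm sites (Sections 8.2 and 8.5), used only to shape the simulation.

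**Formulae**

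ITT = p·d + (1-p)·s

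IV estimate = ITT / p = d + s(1-p)/p

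Ratio to the true user effect, with r = s/d: 1 + r(1-p)/p

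**Size under assumed values**

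| Uptake p | (1-p)/p | Ratio, r = 0.10 fixed | Ratio, r = 0.5p |
|---|---|---|---|
| 80% | 0.25 | 1.025 | 1.10 |
| 50% | 1 | 1.10 | 1.25 |
| 20% | 4 | 1.40 | 1.40 |
| 10% | 9 | 1.90 | 1.45 |

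The last column lets spillover grow with uptake, since more remote follow-up frees more slots. There the ratio is 1 + 0.5(1-p). A harmful spillover would pull the estimate the other way (0.60 at 20% uptake for r = -0.10), but the documents hypothesise only benefit.

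**Simulation of linear 2SRI** (all assumed: 24 sites in 8 steps of 3, 9 periods, 60 patients per site-period, fixed site and period effects, d = -5 days, 150 runs per setting)

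| p | s (days) | IV formula | 2SRI mean (Monte Carlo SE) | ITT formula | ITT mean |
|---|---|---|---|---|---|
| 10% | 0 | -5.00 | -5.10 (0.22) | -0.50 | -0.51 |
| 10% | -1 | -14.00 | -13.62 (0.24) | -1.40 | -1.35 |
| 20% | 0 | -5.00 | -5.05 (0.12) | -1.00 | -1.00 |
| 20% | -1 | -9.00 | -9.33 (0.11) | -1.80 | -1.86 |
| 30% | 0 | -5.00 | -5.14 (0.08) | -1.50 | -1.54 |
| 30% | -1 | -7.33 | -7.28 (0.07) | -2.20 | -2.19 |

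One setting (20%, -1) lies 0.33 / 0.11 = 3 Monte Carlo standard errors from the formula. The overall pattern still follows it: little or no bias without spillover, marked overstatement with it, and an ITT close to its target throughout.

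**Where the bias can arise**
- *New patients.* p = 0, so ITT / p is undefined and no biased number results. The ITT there is 0·d + 1·s = s, which is the capacity effect that Section 8.4 wants to measure.
- *Established patients.* The formula applies only if established non-users also gain. Section 8.1 speaks of other patients in general; Section 8.4 names new patients. Gain among established non-users is an inference.
- *New and established pooled.* Bias would follow from the hypothesis in Section 8.4, but Section 8.2 describes a stratified outcome and no pooled complier analysis is stated.

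**The case for a change.** The case for a change is a good one. The conflict lies within the protocol itself: it plans an estimate that is valid only if a hypothesised effect is absent, states no such assumption, exempts no app or stratum, and calls the result the better measure of efficacy. The algebra is right. Correction would need only wording, because the ITT uses the same data. Nor does the statement that the plan was not followed prove that no complier effect was ever computed.

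Most of this stands as a comment on method. It falls short as a reason to amend, on four counts.

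- The current text retires the Aim 1 plan and names another analysis. Rewording a retired paragraph alters no result that the documents foresee.
- Section 8.13 asks for a brief summary, and the application says that Aim 1 is not its focus. Aim 1 data are analysed by a separate VA centre under its own IRB approval. Silence here on assumptions is weak evidence of an analytical error.
- Section 8.13 does not say which outcomes or strata the complier effect covers, nor that treatment means use of the app rather than teledermatology in general. To fault it for new patients and clinic-level proportions is to criticise analyses that the text does not specify.
- Whether to drop such an estimate or report it with its assumption stated is a choice on which statisticians reasonably differ.

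**Conclusion.** The concern is sound in principle and leads to no change in the plan. A My Telederm complier effect would overstate the user effect by s(1-p)/p if non-users in the analysed group gain from freed capacity. Whether they do is unknown: Sections 8.1 and 8.4 both put the capacity benefit in conditional terms, and both s and p are assumed here. The illustrative overstatement runs from 2.5% to 90% with s at 10% of the user effect and uptake from 80% down to 10%, which shows sensitivity rather than a likely error.

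Against that, the analysis was set aside, the documents do not show that a complier effect was estimated, and the planned ITT captures direct and capacity effects together without this assumption. Should a My Telederm complier effect ever be reported, sensible practice is to present it as secondary to the ITT with the no-spillover assumption stated, and to rely on the ITT alone for new-patient and clinic-level outcomes. An analyst would meet the new-patient limit in any case, since uptake there is zero. For VA Telederm the protocol states no comparable benefit to non-users, and nothing follows for that app.
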